10.5. Planned Analyses

The following 13 preliminary analyses will be conducted for STR review:

1. When all participants in Cohort 1 complete Week 8 (Injection 2 Day 28/Week 4 follow-up) assessments (*results of this analysis will determine Cohort 5 dose and dosing schedule*);
2. When all participants in Cohort 1 & Cohort 2 complete Week 4 (Injection 1 Day 28/Injection 2 Day 1) assessments (*results of this analysis will determine if optional Cohort 4 will proceed and the dose/dosing schedule*);
3. When all participants in Cohort 2 complete Week 8 (Injection 2 Day 28/Week 4 follow-up) assessments;
4. When $\geq 50\%$ participants in Cohort 4 complete Injection 1 Day 10 assessments following Injection 1, data on injection site reactions will be reviewed prior to proceeding with Cohort 5 Injection 1;
5. When 50% participants in Cohort 4 complete Week 8 (Injection 2 Day 28) assessments PK and safety data will be reviewed;
6. When all participants in Cohort 3 & Cohort 4 complete Week 8 (Injection 2 Day 28/Week 4 follow-up) assessments;
7. When all participants in Cohort 4b complete Week 8 (Injection 2 Day 28) assessments, PK and safety data will be reviewed;
8. When $\geq 50\%$ participants in Cohort 4h complete Week 4 (Injection Day 28) assessments, PK and safety data will be reviewed;
9. When all participants in Cohort 4h complete Week 4 (Injection Day 28) assessments, PK and safety data will be reviewed;
10. When $\geq 50\%$ participants in Cohort 5 complete Injection 1 Week 4 assessments, the safety and PK data will be used to determine the dose for Injection 2;
11. When all participants in Cohort 5 complete Week 12 (Injection 1 Week 12 /Injection 2 Day 1) assessments (*results of this analysis will determine if optional Cohort 6 will proceed and the dose/dosing schedule*);
12. When all participants in Cohort 5 complete Week 24 (Injection 2 Week 12/Week 12 follow-up) assessments;
13. When all participants in Cohort 5 & Cohort 6 (if conducted) complete Week 24 (Injection 2 Week 12/Week 12 follow-up) assessments.

The timing or number of preliminary analyses above may be modified based upon emerging data, for example if the planned dosing for a cohort is modified following an STR review due to safety pausing criteria described in Section 7.1 being met, the timing

of the analysis may be modified accordingly.

A further unblinded preliminary analysis will be conducted when all participants in Part 1 Cohorts 1, 2, 3, 4 complete the 8-week Injection Phase to support an abstract submission of key results to a scientific conference.

At least two formal analyses will be conducted:

1. Injection Phase complete: when all participants in Part 1 Cohorts 1, 2, 3, 4 and 4b complete the 8-week Injection Phase, all Cohort 4h participants complete the 4-week Injection Phase and all participants in Part 2 complete the 24-week Injection Phase.
2. End of Study: when all subjects complete the 52-week Follow-up Phase in Part 1 and Part 2.

The Injection Phase complete and End of Study formal analyses will be described in separate clinical study reports.

Each contributing cohort will be unblinded for the purpose of conducting the above formal analyses (after all participants in the cohort complete the injection phase); however, participants and investigators will remain blinded to treatment allocation until each participant in the cohort completes the 52-week Follow-up Phase.

If the recruitment time is prolonged, a formal unblinded interim analysis of data from Cohort 4b and/or Cohort 4h (i.e. prior to all participants in the cohort completing the injection phase) may be conducted to support timely dissemination of study results. The decision to conduct an interim analysis and planned analyses will be documented before unblinding treatment allocations. To minimise bias, the interim results will not be shared with any participants and investigators. However, when investigators are identified as authors of a potential conference presentation of interim results, those investigators and the other co-authors will have access to the interim results prior to its presentation. No other investigators will have knowledge of these data prior to the last participants completing their last visits for the injection phase. An interim analysis abstract may be submitted to a conference for consideration only if the conference convenes after all data collection for the injection phase has been completed. In order to avoid inflation of type I error, no formal statistical analyses evaluating treatment comparisons will be performed for the interim analysis.

Once all participants in Cohort 1 complete 8 weeks post-injection 1, PK (trough concentrations [C_τ] and Plasma AUC_{0-t}), safety and tolerability data will be reviewed along with any safety and tolerability data available at this time from Cohorts 2-3 to determine the dose and dosing schedule for cohort 5 in Part 2. This will be determined by the STR with the aim of selecting a safe dose predicted to achieve approximately 95% of dosed participants having trough concentrations higher than the Phase 3 benchmark for future efficacy studies.

An interim analysis will be performed once all participants in Cohort 1 and Cohort 2 complete their Week 4 assessments post-injection 1. This interim analysis will inform the need for optional Cohort 4 and its dose/dosing schedule and will be based upon review of PK data and all available safety and tolerability data.

An interim analysis for Cohort 5 of PK and safety data up to 4 weeks after the first injection ($\geq 50\%$ participants) and 12 weeks after the first injection, including a review of available PK, safety and tolerability data from cohorts 1-5, will be undertaken to determine the dose for Injection 2 in Cohort 5 and to determine the need for and dose/dosing schedule for Cohort 6, respectively.

11. SUPPORTING DOCUMENTATION AND OPERATIONAL CONSIDERATION REGULATORY, ETHICAL, AND STUDY OVERSIGHT CONSIDERATIONS

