GSK's Global Clinical Safety and Pharmacovigilance (GCSP) staff may unblind the intervention assignment for any participant with an SAE. If the SAE requires that an expedited regulatory report be sent to one or more regulatory agencies, a copy of the report, identifying the participant's intervention assignment, may be sent to investigators in accordance with local regulations and/or GSK policy.

For STR meetings, PK data will be reviewed by treatment arm using scrambled subject identifiers to conceal randomized treatment assignments for subjects with on-going injection phase participation. Safety and tolerability data for a cohort will not be reviewed by treatment arm until all subjects in the cohort have completed the injection phase visits. For the preliminary interim analysis when $\geq 50\%$ participants in Cohort 5 complete Injection 1 Week 4 assessments (see Section 10.5), the analysis and presentation of PK results will be limited to data obtained from the first 9 active treatment and first active control participants based on timing of first injection (this will mask whether 2 vs 1 active control participants will have completed Week 4 assessments at the time of the interim analysis). Additional randomization details are provided in Section 4.1.1 and Section 4.1.2.

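### The author exception lets investigators see unblinded Cohort 4b/4h interim results before the last injection-phase visits, with no earliest access date and no bar on their continuing to assess participants

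*Protocol*

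**What the plan says.** If recruitment is slow, Protocol 10.5 permits "a formal unblinded interim analysis of data from Cohort 4b and/or Cohort 4h (i.e. prior to all participants in the cohort completing the injection phase"). The general rule is strict: "To minimise bias, the interim results will not be shared with any participants and investigators". An exception follows for investigators who are authors of a conference presentation: "those investigators and the other co-authors will have access to the interim results prior to its presentation". For everyone else, "No other investigators will have knowledge of these data prior to the last participants completing their last visits for the injection phase". An abstract may be submitted "only if the conference convenes after all data collection for the injection phase has been completed". The section adds that "no formal statistical analyses evaluating treatment comparisons will be performed for the interim analysis". SAP 3.2 repeats all of this.

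For the formal analyses, the same protocol section says that "participants and investigators will remain blinded to treatment allocation until each participant in the cohort completes the 52-week Follow-up Phase".

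SAP 3.2 also records an additional unblinded interim of Cohorts 1-5 that the sponsor has decided to run. In it, Cohort 4b stays blinded to mitigation treatment and is not shown by mitigation group. All other cohorts are unblinded. They will have finished their injection-phase assessments, but follow-up is described as complete only for Cohorts 1-3.

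**The concern.** The study is double-blind for participants and investigators, and safety and tolerability of the two Cohort 4h arms are stated objectives. ISR grading uses measured area together with the effect on usual activities (Protocol 8.2.6). Intensity and causality of adverse events are investigator judgements (Protocol 11.3.3). Some withdrawal and pausing rules also depend on the investigator's view of relatedness (Protocol 7.1).

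An investigator who has seen unblinded interim results, and who then assesses the rest of the same cohort, may hold an expectation about the treatments that blinding is meant to prevent. The plan recognises this when it withholds interim results from investigators. The exception reopens the route for some of them without a replacement safeguard.

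**Working it through.** The plan states no figure on this point, so there is nothing to recompute. The check is to set the provisions side by side.

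1. **When the interim can fall.** Its definition places it before the cohort finishes the injection phase, and the trigger is prolonged recruitment. Participants may therefore still be entering. Cohort 4h participants are randomised on injection Day 1, and Cohort 4b participants receive a second injection four weeks after the first.

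2. **Who sees results, and when.** The rule excludes all investigators and the exception readmits authors. The sentence beginning "No other investigators will have knowledge of these data prior to the last participants completing their last visits for the injection phase" confirms by contrast that authors may know the data before the last injection-phase visits.

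3. **What the conference condition limits.** It fixes when the meeting may convene. An abstract has to be written and submitted before the meeting, so author access can come before the end of injection-phase data collection.

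4. **What is shown.** The analysis is called unblinded, and the section speaks of documenting decisions before allocations are unblinded. Only formal treatment comparisons are excluded; descriptive summaries by arm are not. Equally, the text does not say that by-arm tables, arm counts or individual allocations go to authors.

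5. **How other provisions treat the same risk.**

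| Provision | Who | Earliest by-arm view |
|---|---|---|
| Protocol 6.3, safety data at Study Team safety & PK Review (STR) meetings | Review team | After everyone in the cohort has completed injection-phase visits |
| Protocol 6.3, project physician lead (Cohort 4b excepted) | Sponsor | Same |
| Protocol 10.5, formal analyses | Investigators | After the cohort's 52-week follow-up |
| SAP 3.2, Cohort 1-5 interim, Cohort 4b | Recipients of the displays | Not shown by mitigation group |
| Protocol 10.5 and SAP 3.2, 4b/4h interim | Author-investigators | No date stated; may precede the last injection-phase visits |

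The last row is the only one with neither a date nor pooling. It leaves author-investigators, who may be assessors, under a looser rule than the sponsor's own review team. Protocol 6.3 also has drug given by site staff who take no part in assessments, but nothing similar separates authors from assessment.

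6. **Cohort 4h at the Cohort 1-5 interim.** Cohort 4h is unblinded there. SAP Tables 2.5 and 2.38 (Cohort 4h ISRs) and Listing 17 (all adverse events) are among that interim's deliverables. Protocol 1.3.4 continues ISR and adverse event assessment in Cohort 4h to Week 52, and the SAP does not say that this follow-up is complete. If author-investigators receive these outputs, that does not sit with an investigator blind lasting to the end of follow-up. The SAP does not say whether they do.

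**The case against.** The strongest reply is that the exposure is conditional and largely dealt with in practice. The interim is optional and the exception applies only to authors. It is a declared trade-off for timely publication. In the interim the SAP actually plans, Cohort 4b is not shown by mitigation group and Cohort 4h has finished its injection-phase assessments. The 52-week sentence is attached to the formal analyses and concerns treatment allocation, so aggregate interim results do not contradict it directly. Erythema and swelling are graded largely on measured area. In Cohort 4b each participant receives both topical treatments in sequence, with placebo applications (SAP 10.2.1), so aggregate results do not identify the current treatment. The primary endpoints are plasma PK, and no formal hypothesis is tested in the main design.

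Most of this stands and limits the point. It does not remove the standing permission, which sets no date and no separation from assessment.

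Three stronger readings are tempting but unsupported:

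- **That the rule breaks the blind.** By-arm display to authors is inferred from the word unblinded, and that authors grade reactions is an assumption.
- **That remaining assignments become guessable.** Aggregate results do not disclose individual allocations, and block size is not stated. With small blocks, arm counts taken at the end of a block are always balanced and reveal nothing. The Cohort 5 precaution in Protocol 6.3 ("this will mask whether 2 vs 1 active control participants will have completed Week 4 assessments") answers a 20:2 allocation, so it is a weak analogy for the 1:1 allocation in Cohorts 4b and 4h.
- **That half of Cohort 4h is exposed.** The 50% threshold belongs to a separate STR preliminary analysis in Protocol 10.5. Protocol 6.3 bars by-arm safety review at STR meetings until injection-phase visits are complete. The 4b/4h interim rule gives no information fraction.

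**Conclusion.** The point holds as a gap in the standing interim rule. Author-investigators may see unblinded Cohort 4b and/or 4h results before the cohort's last injection-phase visits, and nothing keeps them from continuing to assess participants. Their blind can be compromised for judgement-based ISR and adverse event outcomes; the documents do not show that it will be.

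The reach is limited to Cohort 4b (24 participants) and Cohort 4h (about 20), and within them to those assessed after an author-investigator has seen results. That number cannot be derived from the plan. Plasma concentrations are little affected.

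The conclusion assumes that the optional interim is run before injection-phase completion, that at least one author is an investigator who still assesses participants, and that what authors receive distinguishes the randomised groups. The Cohort 4h follow-up point depends further on author-investigators receiving the Cohort 1-5 outputs. This is a cheap improvement to make, not a flaw in the primary PK analysis.

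**What to change.** In Protocol 10.5 and SAP 3.2, qualify the author exception along these lines: while a cohort is still in its injection phase, investigators named as authors receive its interim results only pooled across randomised groups; results by arm are released to them only after that cohort's last injection-phase visit. This extends to Cohort 4h the treatment SAP 3.2 already gives Cohort 4b, and brings the exception into line with the STR rule in Protocol 6.3.

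Also state in SAP 3.2 whether author-investigators receive unblinded Cohort 4h results at the Cohort 1-5 interim, and reconcile the answer with the investigator blind to the end of 52-week follow-up. Either withhold by-arm and participant-level Cohort 4h outputs from them until then, or say explicitly that the blind ends earlier for those individuals.

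The change is wording only. Its cost is that author-investigators see by-arm results later. The delay should be modest for the injection-phase results, because the conference must already convene after injection-phase data collection is complete.

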11.1. Appendix 1: Regulatory, Ethical, and Study Oversight Considerations

11.1.1. Regulatory and Ethical Considerations

- This study will be conducted in accordance with the protocol and with:
 - Consensus ethical principles derived from international guidelines including the Declaration of Helsinki and Council for International Organizations of Medical Sciences (CIOMS) International Ethical Guidelines
 - Applicable ICH Good Clinical Practice (GCP) Guidelines
 - Applicable laws and regulations
- The protocol, protocol amendments, ICF, Investigator Brochure, and other relevant documents (e.g., advertisements) must be submitted to an IRB/IEC by the investigator and reviewed and approved by the IRB/IEC before the study is initiated.
- Any amendments to the protocol will require IEC/IRB approval before implementation of changes made to the study design, except for changes necessary to eliminate an immediate hazard to study participants.
- The investigator will be responsible for the following:
 - Providing written summaries of the status of the study to the IRB/IEC annually or more frequently in accordance with the requirements, policies, and procedures established by the IRB/EC
 - Notifying the IRB/IEC of SAE or other significant safety findings as required by IRB/IEC procedures
 - Providing oversight of the conduct of the study at the site and adherence to requirements of 21 CFR, ICH guidelines, the IRB/IEC, European regulation 536/2014 for clinical studies (if applicable), and all other applicable local regulations

11.1.2. Financial Disclosure

Investigators and sub-investigators will provide the sponsor with sufficient, accurate financial information as requested to allow the sponsor to submit complete and accurate financial certification or disclosure statements to the appropriate regulatory authorities. Investigators are responsible for providing information on financial interests during the course of the study and for 1 year after completion of the study.

11.1.3. Informed Consent Process

- The investigator or his/her representative will explain the nature of the study, including the risk and benefits, to the participant and answer all questions regarding the study.
- Participants must be informed that their participation is voluntary. Participants or their legally authorized representative will be required to sign a statement of informed consent that meets the requirements of 21 CFR 50, local regulations, ICH guidelines, privacy and data protection requirements, where applicable, and the IRB/IEC or study centre.
- The medical record must include a statement that written informed consent was obtained before the participant was enrolled in the study and the date the written consent was obtained. The authorized person obtaining the informed consent must also sign the ICF.
- Participants must be re-consented to the most current version of the ICF(s) during their participation in the study.
- A copy of the ICF(s) must be provided to the participant or the participant's legally authorized representative.
- Participants who are rescreened are required to sign a new ICF.

GSK/ViiV Healthcare (alone or working with others) may use participant's coded study data and samples and other information to carry out this study; understand the results of this study; learn more about CAB or about the study disease; publish the results of these research efforts; work with government agencies or insurers to have the CAB approved for medical use or approved for payment coverage.

11.1.4. Data Protection

- Participants will be assigned a unique identifier by the sponsor. Any participant records or datasets that are transferred to the sponsor will contain the identifier only; participant names or any information which would make the participant identifiable will not be transferred.
- The participant must be informed that his/her personal study-related data will be used by the sponsor in accordance with local data protection law. The level of disclosure must also be explained to the participant who will be required to give consent for their data to be used as described in the informed consent.
- The participant must be informed that his/her medical records may be examined by Clinical Quality Assurance auditors or other authorized personnel appointed by the sponsor, by appropriate IRB/IEC members, and by inspectors from regulatory authorities.

11.1.5. Dissemination of Clinical Study Data

- Where required by applicable regulatory requirements, an investigator signatory will be identified for the approval of the clinical study report. The investigator will be provided reasonable access to statistical tables, figures, and relevant

reports and will have the opportunity to review the complete study results at a ViiV Healthcare/GSK site or other mutually agreeable location.

- ViiV Healthcare/GSK will also provide the investigator with the full summary of the study results. The investigator is encouraged to share the summary results with the study participants, as appropriate.
- ViiV Healthcare/GSK will provide the investigator with the randomization codes for their site only after completion of the full statistical analysis.
- The procedures and timing for public disclosure of the protocol and results summary and for development of a manuscript for publication for this study will be in accordance with ViiV Healthcare/GSK Policy.
- ViiV Healthcare/GSK intends to make anonymized participant-level data from this trial available to external researchers for scientific analyses or to conduct further research that can help advance medical science or improve patient care. This helps ensure the data provided by trial participants are used to maximum effect in the creation of knowledge and understanding.

11.1.6. Data Quality Assurance

- All participant data relating to the study will be recorded on printed or electronic CRF unless transmitted to the sponsor or designee electronically (e.g., laboratory data). The investigator is responsible for verifying that data entries are accurate and correct by physically or electronically signing the CRF.
- The investigator must maintain accurate documentation (source data) that supports the information entered in the CRF.
- The investigator must permit study-related monitoring, audits, IRB/IEC review, and regulatory agency inspections and provide direct access to source data documents.
- Monitoring details describing strategy (e.g., risk-based initiatives in operations and quality such as Risk Management and Mitigation Strategies and Analytical Risk-Based Monitoring), methods, responsibilities and requirements, including handling of noncompliance issues and monitoring techniques (central, remote, or on-site monitoring) are provided in the Monitoring Plan
- The sponsor or designee is responsible for the data management of this study including quality checking of the data.
- The sponsor assumes accountability for actions delegated to other individuals (e.g., Contract Research Organizations).
- Study monitors will perform ongoing source data verification to confirm that data entered into the CRF by authorized site personnel are accurate, complete, and verifiable from source documents; that the safety and rights of participants are being protected; and that the study is being conducted in accordance with the currently approved protocol and any other study agreements, ICH GCP, and all applicable regulatory requirements.

- Records and documents, including signed ICF, pertaining to the conduct of this study must be retained by the investigator for 15 years from the issue of the final Clinical Study Report (CSR)/ equivalent summary unless local regulations or institutional policies require a longer retention period. No records may be destroyed during the retention period without the written approval of the sponsor. No records may be transferred to another location or party without written notification to the sponsor.

